9.2.3 General Statistical Consideration

Statistical analysis for ORR and safety will be performed for subjects given at least one dose of the investigational product. Statistical analyses for PFS, OS will be performed for intention-to-treat population.

Our hypothesis is that combinational treatment with ORR as 30% is superior to historical ORR of a single agent atezolizumab as 15%. To control type I error under one-sided 10%, with power of 80%, we'll use the exact method of one-sample inference for a binomial proportion. For the percentages of CR, PR and SD, the corresponding 95% CI will be estimated using the Clopper-Pearson method for each treatment group.

Final analysis will be done when the last patient enrolled has been treated for 6 months.

The survival estimates will be derived from Kaplan and Meier curves.

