TITLE: A single-arm phase II study of cabozantinib and atezolizumab in patients with recurrent or metastatic esophageal squamous cell carcinoma (ESCC) who failed a platinum-based chemotherapy

一項針對已接受過白金類化療之復發或轉移食道鱗狀細胞癌患者，
合併使用 **cabozantinib** 及 **atezolizumab** 的第二期臨床試驗

Principal Investigator:

[name] M.D., Ph.D. [name] 醫師

Department of Oncology, National Taiwan University Hospital

[name]

[contact] [name]

[contact]

E-mail: [contact]

Co-Investigators:

Department of Oncology, National Taiwan University Hospital

[name].	[name] 醫師
[name].	[name] 醫師
[name].	[name] 醫師
[name].	[name] 醫師
[name]., Ph.D.	[name] 醫師
[name]., Ph.D.	[name] 醫師

Division of Chest Surgery:

[name]	M.D., Ph.D.	[name] 醫師
[name]	M.D., Ph.D.	[name] 醫師

PROTOCOL SYNOPSIS

STUDY TITLE: A PHASE II STUDY OF CABOZANTINIB AND ATEZOLIZUMAB IN PATIENTS WITH RECURRENT OR METASTATIC ESOPHAGEAL SQUAMOUS CELL CARCINOMA (ESCC) WHO FAILED PLATINUM-BASED THERAPY	
STUDY SCIENTIFIC OBJECTIVE	To demonstrate that combination of cabozantinib and atezolizumab is safe and efficacious in patients with recurrent/metastatic esophageal squamous cell carcinoma (ESCC)
STUDY DESIGN	
A single-arm, single-institute, phase II study.
 
The combination of cabozantinib and atezolizumab:
 
• Cabozantinib 40 mg, PO, QD;• Atezolizumab 1200 mg, IV, Q3W;• Treatment will be continued until intolerable toxicities occur and/or patients no longer derive clinical benefits from the treatment. 
Evaluation and follow-up:
 
• Clinical evaluation including blood sampling: every 3 weeks• Tumor response evaluation: every 9 weeks• Follow-up of potential treatment-related AEs will be continued until 30 days after discontinuing protocol treatment of start of next salvage treatment, whichever comes first.• The planned enrollment number of study subjects is 37.• The ORR of anti-PD-1 mAbs for R/M ESCC patients has been around 15% according to previous studies.• We hypothesize that combination of cabozantinib plus atezolizumab will improve the ORR from 15% to 30%. With one-sided, 0.1 type I error (α), 0.2 type II error (β, corresponding power: 0.8), the sample size will be 37.

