9.2 Statistical Analysis Plan

9.2.1 Sample Size Determination

The target sample size of this prospective, single-arm, phase 2 study is 37 patients. A sample size of 37 achieves 82% power to detect a difference (P1-P0) of 0.15 using a one-sided binomial exact test. The target significance level is 0.1. These results assume that the population proportion under the null hypothesis is 0.15 and the alternative hypothesis is 0.3. The sample size was calculated by PASS. The average number of newly diagnosed ESCC patients at our center is around 180 patients per year. Among them, 30% patients present with metastatic disease and 60% patients present with locally advanced disease. Around 50% of locally advanced ESCC will have recurrent diseases indicated for this study. We plan to enroll 2 patients per month into this trial. Therefore, the estimated duration of total enrollment will be 19 months. With additional follow-up of 6 months after the last enrollment, the whole study period of the trial will be 25 months.

The primary objective of the study is to improve overall response rate for recurrent or metastatic ESCC patients who have failed a platinum-based chemotherapy. The secondary objectives of the study included the median progression-free survival, overall survival, and safety and toxicity. According to the two phase III global clinical trials (KEYNOTE-181 and ATTRACTION-3), the ORR for second-line immune checkpoint inhibitors is around 15%. We estimated the ORR could improve to 30% in the combination of atezolizumab and cabozantinib.

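### Does calling the 15% benchmark the single-agent atezolizumab rate in section 9.2.3, and a class rate elsewhere, undermine the primary hypothesis?

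*Combined protocol and SAP*

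**What the plan says.** Section 9.2.3 (General Statistical Consideration) gives the primary hypothesis: "Our hypothesis is that combinational treatment with ORR as 30% is superior to historical ORR of a single agent atezolizumab as 15" per cent.

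The same figure is described differently elsewhere:

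- Synopsis, under both study design and statistical consideration: "The ORR of anti-PD-1 mAbs for R/M ESCC patients has been around 15% according to previous studies".
- Section 9.2.1 (Sample Size Determination): "According to the two phase III global clinical trials (KEYNOTE-181 and ATTRACTION-3), the ORR for second-line immune checkpoint inhibitors is around 15" per cent.
- Table 9-1 gives 15% as the historical value and names no agent.

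The numerical hypotheses are in section 9.2.1: "These results assume that the population proportion under the null hypothesis is 0.15 and the alternative hypothesis is 0.3". The decision procedure is in section 9.2.3: "To control type I error under one-sided 10%, with power of 80%, we'll use the exact method of one-sample inference for a binomial proportion".

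On interval estimates, section 9.2.3 says: "For the percentages of CR, PR and SD, the corresponding 95% CI will be estimated using the Clopper-Pearson method for each treatment group". The overall response rate, which is the sum of CR and PR, is not in that list.

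**The concern.** With no control arm, the historical rate is the whole comparison. Rejecting 15% shows that the response rate on the combination exceeds 15%. What that means depends on whose rate 15% is. If it belongs to anti-PD-1 antibodies or to checkpoint inhibitors as a class, a success says that the combination beats a class benchmark. If it belongs to atezolizumab alone, a success can be read as evidence that cabozantinib adds to its partner drug, which is a stronger statement. Section 9.2.3 uses the second description, while the only sources named for the 15% support the first. Because the sentence stands next to the specification of the primary test, a report could quote it directly.

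A smaller worry concerns the intervals. The primary endpoint is missing from the list of quantities that get one. A 95% interval would also not line up with a one-sided 10% test, so a positive trial might be reported with an interval that includes 15%.

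**Working it through.** **Inputs.** n = 37, p0 = 0.15 and p1 = 0.30 (section 9.2.1); one-sided level 0.10 and an exact one-sample binomial test (sections 9.2.1 and 9.2.3).

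**Step 1: reproduce the stated power.** The success threshold is the smallest r with P(X ≥ r | n = 37, p = 0.15) ≤ 0.10. Power is P(X ≥ r | n = 37, p = 0.30).

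| r | r/37 | P(X ≥ r) at 0.15 | P(X ≥ r) at 0.30 |
|---|---|---|---|
| 8 | 21.6% | 0.181 | 0.905 |
| 9 | 24.3% | 0.092 | 0.824 |
| 10 | 27.0% | 0.042 | 0.711 |

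The threshold is 9. The exact type I error is 9.2% and the power 82.4%, which agrees with the plan: "A sample size of 37 achieves 82% power to detect a difference (P1-P0) of 0.15 using a one-sided binomial exact test".

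**Step 2: change the label.** The calculation uses only n, p0, p1 and the level. All the descriptions give 15%, so replacing one by another leaves p0, the sample size, the threshold, the error rate, the power and the p-value for any observed count as they are.

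**Step 3: set the descriptions side by side.** The term in section 9.2.1, immune checkpoint inhibitors, is a class that can include atezolizumab. Exclusion criterion 1 likewise treats PD-1 and PD-L1 blockade together. Section 9.2.3 can therefore be read as applying the class rate to the regimen's own checkpoint inhibitor. Only the synopsis, which refers to anti-PD-1 antibodies, clearly differs. Section 9.2.3 also calls the rate historical, which marks it as an external benchmark.

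**Step 4: how much could hang on the label?** The documents available here give no separate rate for atezolizumab, so the following true reference rates are assumptions. The last column is P(X ≥ 9 | n = 37, p).

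| Assumed true reference rate | Chance of declaring success |
|---|---|
| 10% | 0.9% |
| 12% | 2.8% |
| 15% | 9.2% |
| 17% | 16.5% |
| 18% | 21.0% |
| 20% | 31.4% |

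The spread is wide, but it is the spread for any single-arm trial whose benchmark may be off by a few points. It would be the same if the benchmark were called a class rate. Rewording would not narrow it.

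**Step 5: the intervals.** Clopper-Pearson lower limits are the α/2 quantile of Beta(r, 38 − r), where 38 = n + 1.

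| Responses | One-sided p | Two-sided 80% lower limit | Two-sided 95% lower limit |
|---|---|---|---|
| 8 | 0.181 | 13.0% | 9.8% |
| 9 | 0.092 | 15.2% | 11.8% |
| 10 | 0.042 | 17.5% | 13.8% |
| 11 | 0.017 | 19.8% | 15.9% |

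With 9 or 10 responses the trial succeeds although the 95% interval includes 15%. That reflects the different levels of the two procedures. The plan bases the decision on the exact test and nowhere makes the interval decide.

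**The case for a change.** The best argument for acting is that the benchmark is the entire comparator and that section 9.2.3 is where readers will look for the hypothesis. Naming a component of the regimen invites a claim about cabozantinib's contribution, and no section available here supplies or sources the rate that claim would need. The 10% error control holds for a reference rate of 15%; it holds for atezolizumab alone only if that drug's rate is no higher than 15%. Harmonising the text would cost only words.

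Part of this stands. The descriptions do differ, and a report that claimed superiority over atezolizumab alone would need its own support. But no section available here plans such a conclusion. The synopsis objective is that the combination is safe and efficacious, and section 9.2.1 speaks of improving the response rate. The background sections were also not available, so a source for an atezolizumab rate, or a justification for borrowing the class rate, cannot be ruled out; to insist that the wording be withdrawn would go beyond the evidence.

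On the intervals, the omission of the overall response rate is real. But an analyst already producing Clopper-Pearson intervals for CR and PR would compute one for their sum as a matter of course. Choosing 80% over 95% is a preference about presentation.

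**Conclusion.** No change to the plan follows. The 15% is described inconsistently, most clearly between section 9.2.3 and the synopsis, but this is a clerical matter. The null value of 0.15, the 37 patients, the threshold of 9 responses, the 9.2% type I error and the 82.4% power are identical under every description, and so is the outcome of the test for any observed count. Harmonising the wording would bring no statistical gain. The missing interval for the overall response rate is a gap that analysts fill sensibly.

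This rests on two conditions: that 15% remains the tested null, as every section states, and that all 37 patients are analysed. Section 9.2.3 limits the primary analysis to dosed patients: "Statistical analysis for ORR and safety will be performed for subjects given at least one dose of the investigational product". Fewer dosed patients would alter the operating characteristics slightly (with 36, the threshold is still 9, the type I error 8.0% and the power 79.6%), again whatever the 15% is called. What a success may be said to show is a matter for the report: a response rate above a 15% historical benchmark.
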